Similar, effective results have been published in paediatric spinal deformity surgery. Grant *et al*, in a retrospective case-control series, showed a high dose TXA regimen (20mg/kg load, 10mg/kg/hr infusion) reduced blood loss and transfusion requirements when compared with a low dose TXA regimen (10mg/kg load, 1mg/kg/hr infusion). Unfortunately, the study was underpowered (High Dose TXA: 15, Low Dose TXA: 11) to detect a significant difference. Sethna *et al* showed a significant reduction in blood loss ( $p<0.01$ ) in paediatric patients undergoing spinal fusion for scoliosis. In both series, no complications were reported related to TXA use.

There is no appropriately powered study comparing two TXA dosing regimens in a homogenous patient population. This study will provide high quality evidence for or against the use of a high dose TXA regimen in adult spinal deformity patients, in addition to supporting the safety profile of TXA in this patient population.

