### Research Design and Methods

Study Design: Randomized, double blind, controlled Trial at a single institution. The study will be registered at [www.ClinicalTrials.gov](http://www.ClinicalTrials.gov) .

**Power Analysis:** We anticipated an intraoperative estimated blood loss (EBL) of 2,000mL with a standard deviation of 500mL in the control group. A difference of 400mL was estimated to be a clinically relevant difference, as differences in excess of 400mL may result in additional units of allogeneic packed red blood cell transfusion during and after surgery. A sample size of 26 patients per group (52 total) was needed to find a difference of 400mL with a power of 80% and alpha defined as 0.05. In anticipation of nonadherence and loss to follow up, target enrollment was 60 patients.

**Selection Protocol:** Following Institutional Review Board (IRB) approval, adult patients (ages 18-75) scheduled to undergo long segment (Upper Instrumented Vertebra (UIV) T5 or proximal and Lower Instrumented Vertebra (LIV) L3 or distal) posterior spinal fusion with instrumentation (PSF) for adult scoliosis without a current deep venous thrombosis (DVT), TXA related contraindications, or other distinct contraindications are eligible and consent for participation will be sought.

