#### Contraindications to Enrollment

1. Any patient who pre-donates autologous blood for intra- or postoperative use. (Directed donor units are acceptable).
2. Any patient with history of suspected blood disorders or abnormal coagulation laboratory results.
3. Any patient on anticoagulation therapy that cannot be interrupted.
4. Any patient with history of deep vein thrombosis (DVT).
5. Any patient with impaired renal function or serum creatinine > 1.5.

All eligible patients will be provided with a detailed explanation of the study as well as a copy of an Investigational Review Board (IRB) approved informed consent form to take home and review. Only after all patient questions have been answered and the patient is agreeable to participation, will an informed consent be obtained. A study coordinator will obtain and complete baseline data forms.

**Patient Randomization:** After consent is obtained and the patient is enrolled in the trial, patients will be assigned deidentified, unique ID numbers. Randomization of these IDs to either low or high dose tranexamic acid will occur via a computer generated random assignment. Given the variations that may exist in surgical technique (e.g. performance of osteotomies), stratified randomization will be performed by attending surgeon. Based upon the randomization, the pharmacy will prepare tranexamic acid (TXA) for one of two intravenous dosing protocols(independent variable): (1) Low Dose(Standard of Care/Control): Loading Dose 10mg/kg given over 15 minutes, followed by 1mg/kg/hr via continuous infusion (2) High Dose(Study Group): Loading Dose 100mg/kg given over 15 minutes, followed by

10mg/kg/hr via continuous infusion. The medications will be delivered to the operating room in identical packaging for both treatment groups, and labeled "TXA Study Drug." All patients will receive a test dose prior to the induction of general anesthesia. The surgeon, anesthesia team, and operating room staff will be blind to the concentration of TXA in the medications received. Treatments may be "unblinded" at the discretion of the surgeon and anesthesiologist, in cases of extreme blood loss. If additional anti-fibrinolytics are given, the change in dose will be recorded. The loading dose will be given to coincide with incision. The continuous infusion will be stopped at the conclusion of fascial layer closure.

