18. Visual Analog Pain Score

Intraoperative data collected will include:

1. Procedure Length (Incision to Skin Closure, minutes)
2. Levels Fused
3. Levels of Instrumentation and Type
4. Osteotomies Performed (Yes / No / Type)
5. Hemoglobin Concentration at Incision, Closure (by Arterial Blood Gas)
6. Estimated Blood Loss (estimated as three times cell saver volume)
7. Crystalloid / Colloid Volume Infused
8. Allogeneic Packed, Red Blood Cells (PRBC) / Fresh Frozen Plasma (FFP) / Platelets (PLT) Transfused
9. Urine Output
10. Intraoperative Surgical Complications

Postoperative data collected will include:

1. Drain Output (with Length of Drain Use)
2. CBC on Postoperative Days #1,2, and 3
3. Units of PRBC / FFP / PLT Transfused
4. Length of Hospital Stay
5. Disposition at Discharge
6. Acute Perioperative Complications
7. Duplex Ultrasound Scan of Lower Extremities Result

Followup visits will be six weeks and three months to capture complications potentially related to TXA at up to three months after surgery. At these visits, SRS-22 and ODI scores will be obtained. The dependent variables of interest are:

1. Intraoperative and Total Estimated Blood Loss
2. Number of PRBC Units Transfused
3. Intraoperative and Acute Complications (up to three months)

All findings will be reported using CONSORT guidelines.

Human Subjects

All protocol violations will be reported to the Washington University IRB. All serious adverse events (SAE's) will be reported to the Washington University IRB within 15 days of occurrence. SAE will be tracked and potential association with TXA administration will be determined site PI. Any frequently occurring SAE felt to be associated with TXA administration will be reported to all participating centers as well as Med Watch.

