Low versus High Dose Tranexamic Acid in Adult Spinal Deformity Surgery: A Randomized, Controlled Trial

NCT 02053363

08/01/2018

Statistical Analysis Plan

Parametric data were expressed as mean \pm standard deviation and compared using the Student t test and Chi-square. Nonparametric data were expressed as median (interquartile range) and compared via the Mann-Whitney U test. Prior to analysis, outlier values were examined to determine their origin and ensure they did not represent data entry errors. Enrollment and surgical data were compared to ensure successful randomization. Data were analyzed on an intention-to-treat basis. Only patients who enrolled and underwent surgery were considered completed. Randomization failures were patients who enrolled but failed to undergo surgery as scheduled and were not randomized. Mean EBL was the primary outcome measure, while number of PRBC transfused, mean number of intraoperative complications and 90-day complications were secondary outcomes. All tests were 2 sided and were considered statistically significant if the P value was less than 0.05. Statistical analysis was performed using JMP, version 13 (SAS Institute Inc., Cary, North Carolina, USA).

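### The protocol expects the trial to support TXA's safety profile, but the SAP plans only P<0.05 comparisons of complications, with no confidence interval for a between-arm difference

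*SAP*

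**What the plan says.** **Stated aim.** The protocol's Background and Significance section presents the trial as giving evidence on the high-dose regimen "in addition to supporting the safety profile of TXA in this patient population".

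**Data collected.** Under Data Collection, the protocol lists as a dependent variable "Intraoperative and Acute Complications (up to three months"), and sets follow-up visits at six weeks and three months "to capture complications potentially related to TXA at up to three months after surgery". The postoperative items include "Duplex Ultrasound Scan of Lower Extremities Result". Under Human Subjects, SAEs are tracked and "potential association with TXA administration will be determined site PI". The only stated use of that judgement is onward reporting to the participating centers and Med Watch.

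**Planned analysis.** The SAP is one paragraph. Its safety content is that "mean number of intraoperative complications and 90-day complications were secondary outcomes". Intraoperative complications are clearly a mean number; the form of the 90-day outcome is not stated. The general methods are the t test, chi-square and Mann-Whitney U, two-sided at P<0.05, with mean and SD or median and IQR as summaries. No confidence interval is mentioned for any outcome, and duplex results, DVT, SAEs and attribution are not mentioned.

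**Size.** The Power Analysis rests on blood loss: 26 per group, and "target enrollment was 60 patients".

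**The concern.** A statement about a safety profile needs to say how large an excess of harm in the high-dose arm is still compatible with the data. A P value does not say that. In arms this small, a non-significant result is likely even when the true risks differ substantially, so it separates a harmless regimen from a harmful one poorly.

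The arms differ tenfold in both loading dose and infusion rate, so harm by arm is a natural question for readers. The protocol collects two items that bear on it closely, the duplex result and the attribution of SAEs to TXA. The SAP gives neither a separate place in the analysis. At stake is how much the trial can say about safety, not its blood-loss result.

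**Working it through.** **Inputs.** From the protocol's Power Analysis: difference 400 mL, SD 500 mL, power 80%, alpha 0.05, 26 per group, target enrollment 60. I assume equal allocation, so 30 per arm at full enrollment and 26 per arm at the calculated minimum. The documents give no complication, DVT or SAE rates, so the event counts and risks below are illustrations.

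**1. The plan's own figure.** Normal approximation: n = 2(1.960 + 0.842)² × 500²/400² = 24.5, so 25 per arm. The exact noncentral t gives power of 79.1% at 25 and 80.7% at 26. The stated 26 is therefore reproduced. It concerns blood loss only.

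**2. One arm with no events.** The exact two-sided 95% upper limit is 1 - 0.025^(1/n).
- n = 30: 11.6%.
- n = 26: 13.2%.
- For comparison, one event in 30 gives an exact interval of 0.1% to 17.2%.

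**3. An unequal split: 5/30 high dose v 1/30 low dose.**
- Chi-square without continuity correction: 60 × (5×29 - 1×25)² / (6 × 54 × 30 × 30) = 2.96, P = 0.085. Fisher's exact P = 0.19.
- Risk difference: 0.1667 - 0.0333 = 0.1333.
- Wilson 95% limits: 0.0734 to 0.3356 for 5/30, and 0.0059 to 0.1667 for 1/30.
- Newcombe lower limit: 0.1333 - √[(0.1667 - 0.0734)² + (0.1667 - 0.0333)²] = -0.029.
- Newcombe upper limit: 0.1333 + √[(0.3356 - 0.1667)² + (0.0333 - 0.0059)²] = +0.305.

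The test reports no significant difference. The interval shows that the data are compatible with a slight benefit and with an excess of 30 points.

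**4. Exactly equal arms.** Newcombe 95% half-widths for the difference:

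| Events per arm | Half-width (points) |
|---|---|
| 6/30 v 6/30 (20%) | ±20.2 |
| 12/30 v 12/30 (40%) | ±23.5 |
| 5/26 v 5/26 (19%) | ±21.5 |
| 10/26 v 10/26 (38%) | ±24.9 |

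**5. How often a real difference would be missed.** At 30 per arm, power to detect true risks of 5% v 15% is 25% by the normal approximation and 9% by exact Fisher. For 20% v 40% it is 39% and 30%. Under these assumed risks a non-significant result is the likely outcome despite a doubling or tripling of risk.

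**The case against.** **Much of the SAP's silence can be read generously.** It names two complication outcomes. Chi-square is among its tests, so 90-day complications may already be compared as patients affected. A DVT seen on duplex, or an SAE, may already be counted by arm within 90-day complications. A reader might infer that the plan makes no by-arm use of these data at all. The documents do not support that: they leave it open, and only the absence of a separate table can be asserted. The source cited for the complication items cannot be consulted here. What stands is that even a chi-square comparison of proportions, as planned, yields a P value and no interval.

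**The mean count may be less harmful than it looks.** A reader might infer that averaging complications would conceal a difference in patients harmed. One can construct such a case: 12 patients with one complication each v 4 patients with three each, in arms of 30. Both means are 0.40 and the t test gives P=1.00, yet 40% v 13% of patients are affected. The SAP could, however, send such skewed data to Mann-Whitney, which gives P=0.07, and nothing in the documents makes this pattern likely. I do not rest the point on it.

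**The imprecision comes from arm size.** True: the widths in steps 2 to 4 of the working follow from 26 to 30 patients per arm, and an interval displays that imprecision without reducing it. A reader might infer that the trial is too small. That does not follow, because it was sized for blood loss and that calculation reproduces. Displaying the imprecision is the purpose of the change.

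**The safety aim is a subordinate clause in the background.** It carries no safety hypothesis or margin. A reader might infer that a non-significant P will be presented as proof of safety; neither document says so. The narrower point stands: the planned output supports such a statement only weakly.

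**CONSORT reporting is promised.** The protocol makes this commitment in general terms. It does not specify which safety estimate the analysis will produce.

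**Conclusion.** The concern holds in a limited form. The protocol names support for TXA's safety profile as a product of the trial. The SAP's comparative safety analysis consists of significance tests on two complication outcomes, with no interval for a between-arm difference and no separate by-arm table of duplex results or TXA-attributed SAEs.

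With 30 per arm, no events still leaves a risk of up to 11.6% (13.2% with 26). A non-significant 5/30 v 1/30 leaves an excess of up to 30.5 points, and equal arms at 20% to 40% leave roughly ±20 to ±23 points. The single-arm limits depend only on arm size and the event count shown. The two-arm figures are illustrations, because no rates are given, and all assume equal allocation.

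This is a cheap improvement to the safety reporting. The primary blood-loss result and its sample size are unaffected.

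**What to change.** 1. **Add estimates beside the listed outcomes.** Keep the SAP's complication outcomes as they are. For each arm, also report the number of patients with at least one complication, intraoperatively and up to 90 days. Give the risk difference (high minus low dose) with its 95% CI, for example Newcombe.
2. **Optional by-arm tables.** Tabulate patients with a positive duplex result and patients with at least one TXA-attributed SAE, with exact 95% CIs. Say whether attribution was made blind to arm. Under Patient Randomization the protocol states that "The surgeon, anesthesia team, and operating room staff will be blind to the concentration of TXA in the medications received", but the site investigator who attributes SAEs is not listed under that title.
3. **Label additions by timing.** The SAP is written in the past tense. Any of the above added after the data were seen, including the patients-affected comparison in item 1, should be marked post hoc.
4. **Limit the safety wording.** Restate the background sentence as an aim to describe complications up to 90 days, and state that a non-significant difference is not evidence of safety.

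**Cost.** A few SAP sentences and one reworded protocol sentence, with no new data, patients or visits. The intervals use standard formulas. The downsides are a more modest safety statement, a little extra analysis and, where it applies, a post hoc label.

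### Randomization is stratified by attending surgeon, but the primary comparison of EBL ignores surgeon and rests on P < 0.05 alone, with no between-arm difference and interval to read against 400 mL

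*SAP*

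**What the plan says.** **Sizing (Protocol, Research Design and Methods, Power Analysis).** The planning values are these: "We anticipated an intraoperative estimated blood loss (EBL) of 2,000mL with a standard deviation of 500mL in the control group". The section then names the effect it wants to detect: "A difference of 400mL was estimated to be a clinically relevant difference". The resulting size, for 80% power at alpha 0.05, reads: "A sample size of 26 patients per group (52 total) was needed to find a difference of 400mL". Target enrolment is 60.

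**Allocation (Protocol, Patient Randomization, printed under Contraindications to Enrollment).** "Given the variations that may exist in surgical technique (e.g. performance of osteotomies), stratified randomization will be performed by attending surgeon". No block size and no number of surgeons are given.

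**Analysis (SAP).** "Mean EBL was the primary outcome measure". Data judged parametric are summarised per arm, then "compared using the Student t test and Chi-square". For data judged otherwise, the SAP has a second route: "Nonparametric data were expressed as median (interquartile range) and compared via the Mann-Whitney U test". The threshold is stated once for every test: "All tests were 2 sided and were considered statistically significant if the P value was less than 0.05".

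Neither document mentions surgeon in any analysis, a between-arm difference, a confidence interval, or the use of 400 mL to read the result. The Protocol's Data Collection section commits in general terms to CONSORT reporting and lists both intraoperative and total EBL as outcomes. The SAP does not say which of the two is primary.

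**The concern.** The protocol expects technique to vary between surgeons and builds that into allocation. If surgeons do differ in blood loss, stratification removes that variation from the true sampling error of the treatment difference. An unadjusted t test still counts it in the standard error. The price is precision: a wider interval and less power than the same 60 patients could give.

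The second part concerns reading the result. The protocol's background section says the trial will provide evidence either for or against high dose. A non-significant P value can accompany an interval that rules out a 400 mL reduction, or one that contains both 0 and 400 mL. Only the first is evidence against a clinically relevant benefit, and the SAP does not say how the two will be told apart.

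**Working it through.** **Inputs.** Difference 400 mL, control SD 500 mL, 26 per group, target 60, alpha 0.05 and 80% power come from the Protocol's Power Analysis. Two-sided testing comes from the SAP. Assumed, because the documents do not say: SD 500 mL in the high-dose arm too, 4 surgeons, and a between-surgeon share r of EBL variance from 0 to 30%.

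**1. The plan's own figure.** The normal approximation gives 25 per arm. Exact two-sided t-test power is 79.1% at 25 and 80.7% at 26, so 26 reproduces. At 30 per arm power is 86.1%.

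**2. Unadjusted half-width.** t(0.975, 2n−2) × 500 × √(2/n).
- n = 26: 2.009 × 138.7 = 278.5 mL
- n = 30: 2.002 × 129.1 = 258.4 mL

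**3. Adjusted half-width.** With arms balanced within surgeon, the residual SD is 500 × √(1−r). With treatment and 4 surgeons the df is 2n−5. At n = 30 this is 258.7 × √(1−r). The unadjusted half-width stays at about 258 mL because its pooled SD still contains the surgeon variance. Unadjusted coverage and power for r above 0 are simulated, with surgeon effects fixed at the stated share.

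| r | Half-width, unadjusted → adjusted (mL) | Coverage of unadjusted 95% CI | Power for 400 mL, unadjusted → adjusted |
|---|---|---|---|
| 0 | 258.4 → 258.7 | 95% | 86% → 86% |
| 10% | 258 → 245 | about 96% | 87% → 89% |
| 20% | 258 → 231 | about 97% | 89% → 93% |
| 30% | 258 → 216 | about 98% | 90% → 95% |

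At 26 per arm the adjusted half-widths are 279/265/249/233 mL for r = 0/10/20/30%.

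**4. Cost if surgeons do not differ.** About 0.3 mL with balanced arms (258.4 to 258.7). If assignment within surgeon is simple rather than blocked, the mean half-width goes from 260.7 to 268.0 mL (60 patients, 4 surgeons), about 7 mL.

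**5. What P < 0.05 leaves unsaid.** Count a reduction on high dose as positive. A non-significant observed reduction excludes 400 mL if it is below 400 − 278.5 = 121.5 mL (26 per arm) or 400 − 258.4 = 141.6 mL (30 per arm). Between 121.5 and 278.5 mL, or 141.6 and 258.4 mL, it excludes neither 0 nor 400. These bounds take the observed SD as 500 mL. Integrating over the sampling distribution of the SD, with no adjustment, gives:

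| True reduction (mL) | CI contains both 0 and 400, 26 per arm | 30 per arm |
|---|---|---|
| 0 | 17% | 11% |
| 100 | 33% | 26% |
| 200 | 41% | 34% |
| 300 | 33% | 26% |
| 400 | 17% | 11% |

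The peak is at 200 mL, midway between the two limits.

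**6. What changes these rates.** Stating the interval labels such results without making them rarer. Adjustment makes them rarer if surgeons differ. At a true 200 mL and 30 per arm, for r = 10/20/30%, the rate falls from 36/38/40% to 28/21/13%. If surgeon effects are drawn at random for each trial, the unadjusted rates are about 34/34/33%. At a true 400 mL it falls from about 9–11% to 8/5/3%.

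**The case against.** The strongest reply is that the planned test is valid and the trial is adequately sized. That stands. A reader might infer from the omitted stratum that false positives are inflated. The opposite holds: coverage above 95% means a type I error at or below 5%. Nor is the trial underpowered on its own assumptions, since 26 per arm reproduces.

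The gain from adjustment rests on inputs the documents do not give. This also stands. At r = 0 there is no gain, and at 10% it is 13 mL of half-width and about 2 points of power. The protocol does, however, state its own expectation that technique varies, and the cost of being wrong is small.

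A reader might infer that no interval will be reported. The documents do not support that. The outcome is called mean EBL and the sizing uses a mean and SD, so the text favours the t test. On that route the unadjusted interval follows from means, SDs and arm sizes, and the CONSORT commitment may lead to its being reported. What is missing is a specified estimate, its adjustment and its reading. If EBL were treated as nonparametric, a median (IQR) and a Mann-Whitney P value would not estimate the mean difference on which the trial is sized.

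Finally, 400 mL is a sizing figure, and neither document makes it a bound to exclude. That is correct: the reading proposed below is an addition, not a rule the SAP has broken. It uses 400 mL because the protocol calls that difference clinically relevant.

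**Conclusion.** The point holds as an inexpensive improvement to a valid plan. The stratification factor should be in the primary model. Under the assumptions of 4 surgeons, SD 500 mL in both arms, 30 per arm, balance within surgeon and a 10–30% variance share, adjustment narrows the half-width by 13 to 42 mL (258 less 245 to 216) and adds about 2 to 5 points of power for 400 mL. At a share near 0 it does nothing useful and costs very little.

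The missing difference and interval is a secondary point and partly a matter of detail. It affects how a non-significant result can be read. The 41%/34% rates are the worst case; at a true 0 or 400 mL they are 17%/11%.

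Two stronger readings should not be drawn. The SAP does not contradict the protocol, since leaving out a stratum is an omission. And the lack of a stated interval does not itself make the trial more likely to be inconclusive.

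**What to change.** State one primary analysis in the SAP: the difference in mean intraoperative EBL (low dose minus high dose, so positive is a reduction) with a two-sided 95% CI, from a linear model with treatment and attending surgeon. Fix one CI method in advance, for example heteroscedasticity-robust, instead of choosing after looking at skewness. The half-widths above are for the ordinary model-based interval, so a robust one will differ somewhat.

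Report the interval against 0 and 400 mL:
- wholly above 400: the reduction exceeds the target
- above 0 and containing 400: reduction shown, its size relative to 400 open
- above 0 and wholly below 400: reduction shown, smaller than the target
- containing 0 and wholly below 400: evidence against a 400 mL reduction
- containing both 0 and 400: inconclusive
- wholly below 0: higher blood loss on high dose

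Keep Mann-Whitney as a sensitivity analysis and name total EBL as secondary, which also settles which EBL is primary.

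The cost is a few sentences and no new data, provided each patient's surgeon is on record, as stratification requires. In precision, the cost is the 0.3 to 7 mL shown above if surgeons do not differ. The SAP is dated 08/01/2018 and written in the past tense. If results are already known, label this analysis post hoc.
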